### 9.3. Sensitivity Analysis

Sensitivity analyses will be based on ITT population and will be performed for primary and secondary efficacy endpoints. This will include the same statistical methodology as in the primary and secondary analyses, however when using imputed data preliminary imputation steps will have to be completed prior to applying the methods from the primary and secondary analyses.

The following analyses will be performed:

- repeating the primary and secondary analyses;

- utilizing LOCF imputed data (see Section 7.3.2.3.1) and analysis of covariance (ANCOVA) model at each visit/time point;
- imputing missing data using multiple imputation techniques (see Section 7.3.2.3.2) and repeating the primary and secondary analyses;
- using Wilcoxon rank sum tests to compare treatments at each time point.

## 10. SAFETY ANALYSES

All Safety analyses will be conducted using the Safety population. Categories for data presentation and analysis will consist of each treatment group (BTQ-1901-A, BTQ-1901-B, BTQ-1902, timolol 0.5%) and overall treatments summary. All safety analyses will be completed using the actual treatment a subject received.

### 10.1. Adverse Events

Adverse events will be coded using the Medical Dictionary for Regulatory Activities (MedDRA), version 23.1.

Treatment-emergent adverse events (TEAEs) are defined as any AE or worsening of an existing condition after initiation of the investigational product and through the subject's last study visit (study completion or early termination). Serious adverse events (SAE) will be recorded from the date of informed consent, throughout the clinical trial. All SAEs that are ongoing at the time of completion or discontinuation from the study will be followed until stabilization or resolution of the event.

If the onset of an AE is on Day 1, then the time of first dose will be compared to the time of onset to determine if the AE is treatment-emergent.

The number and percent of subjects with any TEAEs will be summarized by system organ class and preferred term by dose level (and overall). At each level of tabulation (e.g. at the preferred term level) subjects will be counted only once if they had more than one such event reported during the AE collection period.

The following summary tables and subject level listings will be presented for TEAE data:

- Overall summary of TEAEs
- Summary table of TEAE descending incidence by PT
- Summary table of TEAEs by SOC and PT
- Summary table of serious TEAEs by SOC and PT
- Summary table of TEAEs by highest relationship level to study drug by SOC and PT
- Summary table of serious TEAEs by highest relationship level to study drug by SOC and PT

- Summary table of TEAEs by maximum intensity by SOC and PT
- Summary table of TEAEs leading to study discontinuation by SOC and PT
- Summary table of TEAEs leading to study drug discontinuation or interruption by SOC and PT

Ocular (by study and non-study eye) and non-ocular AE/TEAE will be summarized and listed separately.

## **10.2. Deaths, Serious Adverse Events and Other Significant Adverse Events**

### **10.2.1. Deaths**

All deaths, regardless of causality, will be provided in a table listing and written clinical narratives will also be provided.

### **10.2.2. Serious Adverse Events**

A table listing of SAEs and a table listing of related SAEs will be provided.

Furthermore, the number and percent of subjects with SAEs will be displayed by SOC and PT, and relationship to study medication, for each treatment group. Within each PT, subjects will be counted only once if they had more than one SAE event reported during the treatment period.

### **10.2.3. Adverse Events Leading to Discontinuation of Study Drug**

A table listing of all AEs leading to study discontinuation, or discontinuation/ interruption of study drug will be presented.

Furthermore, the number and percent of subjects with AE's leading to study discontinuation, or discontinuation/interruption of study drug will be displayed by SOC and PT for each treatment group. Within each PT, subjects will be counted only once if they had more than one AE leading to study discontinuation, or discontinuation/interruption of study drug reported during the treatment period.

## **10.3. Bilateral Ophthalmic Examinations**

Bilateral ophthalmic examinations (LogMAR BCVA, slit lamp biomicroscopy, dilated ophthalmoscopy, VF testing) including grading of conjunctival hyperemia by the Investigator and assessment of comfort/tolerability by the subject (drop comfort rating) will be summarized descriptively for each treatment group by time point. Assessments done on both eyes will be summarized separately by study and non-study eye.

Continuous results will be summarized descriptively for the observed value as well as for the change from baseline value. Categorical results will be summarized by counts and percentage.

Unscheduled visit results will not be summarized but will be included in patient data listings.

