9.4.2. Biomicroscopy

A slit-lamp examination will be conducted at each study visit to assess the anterior ocular structures. Abnormalities will be documented as abnormal, non-clinically significant (NCS) or abnormal, clinically significant (CS). Consult the Study Manual for specific details.

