9.4.5. Ophthalmoscopy/Dilated Fundoscopy

Ophthalmoscopy/dilated fundoscopy will be conducted, and the structures will be graded as normal or abnormal, NCS, or abnormal, CS. Consult the Study Manual for specific details.

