9.5. Adverse and Serious Adverse Events

9.5.1. Definition of Adverse Events

9.5.1.1. Adverse Event (AE)

An AE is any untoward medical occurrence in a patient or clinical study subject administered a study medication (pharmaceutical/biological product) that does not necessarily have a causal relationship to this medication. An AE can therefore be any unfavorable and unintended sign (including abnormal laboratory findings), symptom, or disease temporally associated with the use of the study medication, whether or not related to the study medication. Study medication includes the investigational drug under evaluation and the comparator product or vehicle placebo that is given during any phase of the study.

Adverse events are collected from the time the subject signs the ICF through the final study visit. Medical conditions/diseases present before starting the investigational treatment are only considered AEs if they worsen any time after the subject signs the ICF. Abnormal test results constitute AEs only if they induce clinical signs or symptoms or require therapy.

The occurrence of AEs should be sought by open-ended questioning of the subject at each visit during the study. At each clinic visit, study personnel should ask the following question: "Have you had any problems since your last visit?" AEs also may be detected when they are volunteered by the subject during or between visits or through study assessments.

9.5.1.2. **Serious Adverse Event (SAE)**

An SAE is any untoward medical occurrence that at any dose:

- Results in death,
- Is life-threatening,

Note: The term "life-threatening" refers to an event in which the subject was at risk of death at the time of the event; it does not refer to an event which hypothetically might have caused death if it were more severe.

- Results in persistent or significant disability/incapacity (excluding progression/outcome of the disease under study),
- Is a congenital anomaly/birth defect,
- Requires inpatient hospitalization or prolongation of existing hospitalization, or
- Is medically significant, i.e., defined as an event that jeopardizes the health of the subject or may require medical or surgical intervention to prevent one of the outcomes listed above.

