#### 7.3.2.2. Baseline

Except for specific analyses noted later (e.g., IOP), baseline values will be the last observation measured prior to dosing. If a repeat value is measured prior to dosing this value can be used for baseline.

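### SAP 10.3 tabulates slit-lamp and fundus results only as counts per time point, so no planned examination table shows how many subjects had a new or worsened finding

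*SAP*

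**What the plan says.** SAP 10.3 covers the bilateral ophthalmic examinations. They "will be summarized descriptively for each treatment group by time point", and "Assessments done on both eyes will be summarized separately by study and non-study eye". It then splits by type of variable:

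- Continuous: "Continuous results will be summarized descriptively for the observed value as well as for the change from baseline value".
- Categorical: "Categorical results will be summarized by counts and percentage".

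Fundus findings are categorical: under Protocol 9.4.5 "the structures will be graded as normal or abnormal, NCS, or abnormal, CS". Protocol 9.4.2 records slit-lamp abnormalities in the same NCS and CS classes. Both therefore fall under the second rule.

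A baseline exists for both. SAP 7.3.2.2 provides that, outside noted exceptions such as IOP, "baseline values will be the last observation measured prior to dosing". The schedule of procedures has slit lamp at all three Visit 3 time points, and Protocol 10.3.1 lists them ahead of the first instillation. Dilated ophthalmoscopy is done at screening and at Visit 6.

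On adverse events, Protocol 9.5.1.1 states: "Abnormal test results constitute AEs only if they induce clinical signs or symptoms or require therapy".

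**The concern.** Ocular safety is part of the primary objective (Protocol 5.1, SAP 4.1.1), and the suspensions have not been given to humans before (Protocol 4). For the two structural eye examinations, the natural question is how many subjects in each arm developed a finding that they did not have before dosing, or moved to a worse class. The planned tables show how many are abnormal at each time point. That is a different quantity, because it combines abnormalities present before dosing with those that arose later.

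The SAP makes the within-subject comparison elsewhere: for continuous ocular results in 10.3 and for vital signs in 10.4. Neither document plans a shift table, or a count of subjects with new or worsened findings, for slit lamp or fundus. Protocol 11.6 promises only descriptive statistics and frequency distributions for safety data, and SAP 10.5 prespecifies nothing further.

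**Working it through.** The plan states no figure to reproduce here. The check is whether per-time-point counts determine the number of new findings, first between two examinations and then across several.

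**Inputs.** N = 60 per arm (Protocol 6.2). On-treatment slit-lamp examinations: 3 visits (4, 5 and 6) × 3 time points = 9 (schedule of procedures). On-treatment fundus examinations: 1 (Visit 6). The documents give no prevalence of abnormal findings, so the counts below are assumptions, shown over a range. Each line concerns one arm and one eye, with complete data.

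**Step 1: two examinations.** Let a be the number abnormal at baseline, b the number abnormal later, r the number of baseline abnormalities that resolved, and n the number of new ones. Then b = a − r + n, so n = b − a + r. The table gives a and b but not r. Since r lies between 0 and a, and n cannot exceed the N − a subjects normal at baseline,

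max(0, b − a) ≤ n ≤ min(b, N − a).

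| a (baseline) | b (later) | New findings compatible with the table | As % of 60 |
|---|---|---|---|
| 6 | 6 | 0 to 6 | 0% to 10% |
| 12 | 12 | 0 to 12 | 0% to 20% |
| 12 | 14 | 2 to 14 | 3.3% to 23.3% |
| 24 | 24 | 0 to 24 | 0% to 40% |
| 24 | 27 | 3 to 27 | 5.0% to 45.0% |

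These are logical limits, not expected values. They show that the counts alone do not fix n unless r is known. The same applies to movement from NCS to CS, which can be offset by movement the other way.

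**Step 2: several examinations (slit lamp only).** Suppose that nine subjects in an arm, all normal at baseline, each have one transient finding at a different one of the nine time points. Every table then shows 1/60 = 1.7% from this source, while 9/60 = 15% of the arm was affected. No planned examination table adds subjects up over time. For treatment-emergent adverse events (TEAEs), by contrast, SAP 10.1 counts each subject once over the collection period.

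**Step 3: can such a finding appear elsewhere?** TEAE tables include worsening of existing conditions and are split into ocular (by study and non-study eye) and non-ocular events (SAP 10.1). The rule in Protocol 9.5.1.1 quoted above allows an asymptomatic, untreated abnormality to stay out of them. It then remains in the by-subject listings (SAP 7.4.1, 10.5), which give no incidence by arm.

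**The case against.** The case for leaving the plan alone has several parts.

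1. Summaries are by time point, so a baseline row is the natural reading. If no baseline finding resolves, r = 0 and the difference between rows gives the new findings exactly: 24 then 27 means 3. This stands. The gap appears only when old findings resolve, when new ones are transient, or when different subjects contribute to the two rows.
2. New findings are not lost. Protocol 9.5.1.1 lets adverse events be detected through study assessments, and 9.5.3 records those revealed by observation regardless of severity. The protocol does not say whether a slit-lamp observation is a test result or a clinical sign. This stands in part: such findings need not be adverse events, but some will be.
3. SAP 7.4.1 permits expanded descriptive categories and SAP 10.5 permits post-hoc safety analyses without an amendment. True, but a table specified before unmasking carries more weight than one chosen afterwards.
4. Counting the worst of nine slit-lamp examinations will pick up grading noise. True, and in all arms.

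Stronger readings do not hold. A reader might infer that drug-related findings are being hidden; a shift table separates new from old, and attribution still rests on comparing arms. A reader might extend the point to every categorical ocular item. Drop comfort is first rated after the first instillation (Protocol 10.3.1), so it has no pre-dose baseline, and the SAP does not say whether hyperemia grade is categorical. A reader might also want the loss expressed as power or test statistics. No test is planned for these results and the documents give no rates, so no such figure can be supported.

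**Conclusion.** The point holds for slit lamp and fundus. The planned tables give prevalence by arm and time point, not the number of subjects with a new or worsened finding. The size of the gap depends on how often findings resolve or recur, which the documents do not give. At 60 per arm and 12 abnormal at both examinations, it is 0 to 12 subjects. For slit lamp the absence of any total across nine examinations adds to this; for fundus, with one on-treatment examination, only the two-examination limits apply.

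This is a minor weakness in descriptive safety reporting. TEAE tables and listings mitigate it, and primary efficacy is unaffected. It is still worth correcting, because ocular safety is in the primary objective and the data needed are already collected.

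**What to change.** In SAP 10.3 add, for slit lamp and fundus:

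- a baseline-by-visit shift table (normal / abnormal NCS / abnormal CS) by arm and by study and non-study eye;
- the number and percent of subjects whose category is worse than baseline at any scheduled on-treatment examination, by arm and eye.

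Include conjunctival hyperemia only if it is analysed as categorical, and state which it is. Leave out drop comfort.

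Name the baseline. Under SAP 7.3.2.2 it is the last pre-dose examination: 4 PM at Visit 3 for slit lamp, normally screening for fundus. If a time-matched slit-lamp baseline is preferred, write it as an explicit exception to 7.3.2.2.

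The cost is SAP wording and a few more descriptive tables, with no added procedures and no change to the adverse event rules. The any-visit count will include some transient grading fluctuation in every arm, so it should be read beside the shift tables.

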#### **10.4. Vital Signs**

Descriptive statistics of observed values will be presented for vital sign data by scheduled study visit, including systolic blood pressure (mm Hg), diastolic blood pressure (mm Hg), heart rate (beats/min) by treatment group for subjects in the Safety Population. Changes from baseline to each scheduled post-baseline visit will be presented.

All vital sign data by subject will be presented in a listing. Unscheduled visit results will not be summarized but will be included in patient data listings.

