The primary efficacy analysis will be the between-group comparison of the mean IOP values in the study eye at each time point at each of the Visit 4/Day 15, Visit 5/Day 42, and Visit 6/Day 84 visits (ie, a total of 9 between-group comparisons). A hierarchical analysis will be conducted to compare each of the investigational products against the comparator, timolol 0.05%, as follows: (1) BTQ-1902, (2) BTQ-1901B, and (3) BTQ-1901A. To demonstrate noninferiority, the upper limits of the 2-sided 95% confidence interval (CI) for the difference between each comparison should be lower than 1.5 mm Hg at all timepoints. Additionally, the upper limits of the 95% CI should be lower than 1.0 mm Hg for the majority of time points measured (ie, 5 of 9).

Statistical Methods (continued):

All other efficacy, safety, tolerability and pharmacokinetic variables will be analysed using appropriate statistical techniques and summarized descriptively. Full details will be provided in the Statistical Analysis Plan.

Sample Size Justification:

The sample size is not based on a formal sample size calculation; this study is planned to provide sufficient data to power the Phase 3 study.

Table 2:Schedule of Procedures

	Screen- ing	Washout Safety Check ^a	Qı	ıalificati Baseline		Treatment								
Day	-35 to -1	-14 ± 3	3 1 3			15 ± 3			42 ± 3		84 ± 3			
Visit	1	2			4			5			6			
Hour ^b			8:00 AM	10:00 AM	4:00 PM	8:00 AM	2 h post dose	4:00 PM	8:00 AM	2 h post dose	4:00 PM	8:00 AM	2 h post dose	4:00 PM
Informed consent	Х													
Medical/ophthalmic history	Х													
Demographics	Х													
Adverse events ^c	Х	Х	Х	Х	Х	Х	Х	Х	Х	Х	Х	Х	Х	Х
Concomitant medications	Х	X	Х			X			Х			Х		
Urine pregnancy test ^d	Х		Х									Х		
HR/BP ^e	Х			Х			Х			Х			Х	
BCVA (logMAR)	Х	Х	Х			Х			Х			Х		
Grading conjunctival hyperemia ^f			Х			Х			Х			Х		
Biomicroscopy	Х		Х	Х	Х	Х	Х	Х	Х	Х	Х	Х	Х	Х
IOP ^g	Х	Х	Х	Х	Х	Х	Х	Х	Х	Х	Х	Х	Х	Х
Visual field testh	Х											Х		
Gonioscopy ⁱ	Х													
Pachymetry ^j	Х													
Dilated ophthalmoscopy	Х													X
Review eligibility	Х				Х									
Randomization					Х									
Blood collection (PK) ^k							Х						Х	

Table 2:Schedule of Procedures

	Screen- ing							nt						
Day	-35 to -1	-14 ± 3		1			15 ± 3			42 ± 3			84 ± 3	
Visit	1	2		3			4			5			6	
Hour ^b	-	-	8:00 AM	10:00 AM	4:00 PM	8:00 AM	2 h post dose	4:00 PM	8:00 AM	2 h post dose	4:00 PM	8:00 AM	2 h post dose	4:00 PM
Study medication dispensed/redispensed					Х			Х			Х			

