The Sponsor is developing two β -blockers, BTQ-1901 and BTQ-1902, in a unique vehicle composed of one excipient, the inert and anhydrous semifluorinated alkane, perfluorohexyloctane (F6H8). F6H8 is a clear, colorless, chemically inert liquid without pharmacologic activity. Both BTQ-1901 and BTQ-1902 are free of other excipients like oils, surfactants, buffers, and preservatives, and are administered in a multidose bottle rather than a unit dose vial. Due to the low surface tension of F6H8, the resulting eye drops are relatively small, with a volume of approximately 11 μ L/drop.

The active ingredient of BTQ-1901 is nebivolol, a β_1 selective β -blocker. The chief advantage of β_1 selectivity is the absence of β_2 -adrenergic inhibition which minimizes the risk of respiratory side effects. Nebivolol also stimulates nitric oxide release via stimulation of the β_3 receptor which produces a vasodilatory effect (Kuroedov et al, 2004) that may improve blood flow to the optic nerve. While extensively used as a systemic blood pressure medication (Bystolic[®] was approved by the United States [US] Food and Drug Administration [FDA] in 2007 [Bystolic package insert, 2019]), nebivolol has not been evaluated for ocular use as an ocular hypotensive therapy.

The active ingredient of BTQ-1902 is timolol. Timolol was the first topical ocular β -blocker approved by the FDA (1978), and it is still an integral part of the standard of care for glaucoma. Utilizing F6H8 as the vehicle for the BTQ-1901 and BTQ-1902 ophthalmic suspensions allows development of these products as non-preserved suspensions in a multi-dose bottle, thus minimizing tolerability and ocular irritation issues that may arise when eye drops contain preservatives or phosphates. This quality may potentially result in fewer ocular AEs.

Importantly, it is postulated that the resulting drug products might have less systemic absorption and fewer negative systemic AEs because of the smaller drop size.

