11.6. Safety Analyses

The safety of BTQ-1901 and BTQ-1902 will be compared to timolol 0.5% with analysis of safety variables including bilateral ophthalmic examinations (LogMAR BCVA, slit lamp

examination, resting HR/BP, ophthalmoscopy/dilated fundus examination, VF testing), and AEs. The ocular tolerability of study medication will be rated by the subject. Safety data will be presented in tables of descriptive statistics and frequency distribution. All summary tables will be supported with individual subject data listings.

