### **4.1. Study Objectives**

#### **4.1.1. Primary Objective**

The primary objective of the study is to evaluate ocular and systemic safety and the efficacy of BTQ-1901-A, BTQ-1901-B, and BTQ-1902 ophthalmic suspensions in comparison to timolol 0.5% ophthalmic solution in subjects with POAG or OHT.

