#### **10.5. Other Safety Measures**

All collected measures and assessments will be listed. No other safety analyses have been prospectively defined. If, however, after study results are reviewed, they will be fully described and documented in the final clinical study report. The SAP does not need to be amended to complete any other safety measures identified as post-hoc.

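### Systemic safety versus timolol solution is part of the primary objective, but no heart-rate or blood-pressure difference with a confidence interval is planned

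*SAP*

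**What the plan says.** SAP 4.1.1 gives a single objective with a comparator: "The primary objective of the study is to evaluate ocular and systemic safety and the efficacy of BTQ-1901-A, BTQ-1901-B, and BTQ-1902 ophthalmic suspensions", in comparison with timolol 0.5% solution. SAP 4.2.2 lists resting HR and BP among the safety endpoints.

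Protocol 11.6 opens with a comparison: "The safety of BTQ-1901 and BTQ-1902 will be compared to timolol 0.5% with analysis of safety variables", and resting HR/BP is among the variables named. The same paragraph fixes the form of output: "Safety data will be presented in tables of descriptive statistics and frequency distribution". The synopsis takes the same line, saying that the remaining efficacy, safety, tolerability and pharmacokinetic "variables will be analysed using appropriate statistical techniques and summarized descriptively".

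For vital signs, SAP 10.4 plans: "Descriptive statistics of observed values will be presented for vital sign data by scheduled study visit", by treatment group in the safety population, and then: "Changes from baseline to each scheduled post-baseline visit will be presented". SAP 10.5 closes the list: "No other safety analyses have been prospectively defined".

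**The concern.** The objective and the first sentence of Protocol 11.6 are comparative, while the planned HR/BP output is one column per arm. No table shows a BTQ arm minus timolol solution, with or without an interval, and no baseline adjustment is planned.

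HR and BP bear on the case made for the products. Protocol Section 4 names decreased heart rate among the systemic risks of beta-blockers and says "it is postulated that the resulting drug products might have less systemic absorption and fewer negative systemic AEs because of the smaller drop size". If the contrast is not specified, readers must build it themselves from the arm summaries. SAP 10.5 also allows further safety analyses to be added after results are seen, without amending the SAP, so any HR/BP difference reported later would be post hoc. SAP Section 6 says the study is meant to inform Phase 3, and an estimate with its uncertainty serves that purpose better than separate arm means.

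**Working it through.** **1. Is the difference planned anywhere else?**

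- Adverse events (SAP 10.1-10.2): counts and percentages by arm, with no risk difference.
- Ophthalmic examinations (SAP 10.3): descriptive by arm.
- Vital signs (SAP 10.4): observed values and changes from baseline by arm.
- Other safety (SAP 10.5): nothing prospectively defined.
- Plasma concentration (SAP 11): mean differences from timolol with 90% CI. This is a pharmacokinetic endpoint in a 40-subject subset. The timolol arm receives no nebivolol, so as a measure of relative exposure the contrast informs only BTQ-1902.

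No safety variable has a planned between-arm difference or interval.

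**2. Do the data support one?**

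The schedule (Protocol Table 2, SAP Table 1) has HR/BP at screening, at 10 AM on Visit 3, and 2 hours after dosing on Days 15, 42 and 84, for every subject. First dosing follows the 4 PM assessments on Visit 3. Under SAP 7.3.2.2 (last value before dosing) the 10 AM reading is therefore the baseline, at about the same clock time as the later readings. Randomization is unstratified (Protocol 8.2) and stable systemic beta-blockers are allowed (Protocol 7.2, criterion 18), so chance imbalance in baseline HR is plausible and adjustment is useful.

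**3. How precise would it be?**

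The documents give no HR or BP standard deviation, effect size or dropout rate, so there is no stated figure to reproduce. Inputs:

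- n = 60 per arm (Protocol 6.2)
- HR SD 8-12 bpm (assumed)
- correlation r between baseline and follow-up 0.4-0.6 (assumed)

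Common factor: 1.96 x sqrt(2/60) = 1.96 x 0.1826 = 0.3578. The 95% half-widths at one visit are:

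- observed values: 0.3578 x SD
- change score: 0.3578 x SD x sqrt(2(1 - r))
- baseline-adjusted: 0.3578 x SD x sqrt(1 - r^2)

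| SD | r | Observed | Change score | Adjusted |
|---|---|---|---|---|
| 8 | 0.6 | 2.86 | 2.56 | 2.29 |
| 10 | 0.5 | 3.58 | 3.58 | 3.10 |
| 12 | 0.4 | 4.29 | 4.70 | 3.94 |

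The range is about 2.3-3.9 bpm adjusted, against 2.6-4.7 bpm for change scores. The ratio of adjusted to change-score width is sqrt((1 + r)/2): 0.84 at r = 0.4 and 0.89 at r = 0.6. Adjustment therefore narrows the interval by 11-16%, or 0.3 bpm (2.56 - 2.29) to 0.8 bpm (4.70 - 3.94) at the ends of the range.

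Withdrawn subjects are not replaced (Protocol 7.3). With an assumed 20% loss (48 per arm) widths grow by sqrt(60/48) = 1.118, so the adjusted range becomes about 2.6-4.4 bpm. For BP with an assumed SD of 15 mm Hg and 60 per arm, the half-width is about 5.4 mm Hg for observed values and 4.3 mm Hg adjusted at r = 0.6.

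**4. How many intervals?**

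3 variables x 3 visits x 3 BTQ arms = 27.

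**The case against.** The strongest reply is that the SAP does what the protocol asks. A reader who stops at the first sentence of Protocol 11.6 might infer that the SAP breaks a promise. The paragraph goes on to specify descriptive tables and the synopsis agrees, so the SAP's claim of consistency with the protocol (SAP 3.3) holds here. The tension between comparing and describing lies inside Protocol 11.6, and the SAP inherits it. This stands.

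A reader might also infer that only raw values are shown, or that the trial cannot say how large an HR effect is. Neither is supported. SAP 10.4 includes changes from baseline, and SAP 7.4.1 requires n, mean and SD by treatment, from which an unadjusted difference and interval can be derived by hand. What is missing is the prespecified contrast and the precision gained by adjustment.

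The protocol's postulate concerns absorption and systemic adverse events, and other output bears on both: the concentration analysis, the adverse-event tables, and the reporting of clinically significant HR/BP changes as adverse events (Protocol 9.5.3). For nebivolol, the chief advantage claimed is respiratory, which HR and BP do not measure. This limits the weight of the point but does not supply the missing estimate.

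Finally, this is a Phase 2 study without a formal sample size, comparisons outside the primary set are exploratory, and 27 intervals invite readers to check each for zero. That risk is real and calls for clear labelling.

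**Conclusion.** The point holds as a worthwhile, inexpensive improvement and not as an error. A named component of the primary objective is comparative, yet neither Protocol 11.6 nor SAP 10.4 plans an HR or BP difference from timolol solution, and SAP 10.5 rules out a prespecified one elsewhere.

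It would be wrong to say that half of the objective goes unanalysed. The objective covers ocular safety, systemic safety and efficacy; ocular safety is also descriptive, and systemic safety includes adverse events. Nothing here biases the trial or touches the primary efficacy analysis.

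The stakes are prespecification and an interval some 11-16% narrower than one derived from change scores. The bpm figures rest on the assumed SD and correlation and on 60 evaluable subjects per arm.

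**What to change.** In SAP 10.4 add, on the safety population, a repeated-measures model of change in HR, systolic BP and diastolic BP at 2 hours post dose on Days 15, 42 and 84. Include treatment, visit, treatment-by-visit interaction and the Visit 3 10 AM value as covariate. Report each BTQ arm minus timolol solution at each visit with a 95% CI.

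State that this is estimation, that the 27 intervals are descriptive and unadjusted for multiplicity, and that no significance claim follows; this is needed because SAP 7.4.1 applies a 0.05 threshold to all tests. Also say whether early-termination readings, which SAP 7.3.3 assigns to a scheduled visit, enter the model when they were not taken 2 hours after a dose.

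The cost is one SAP paragraph and three tables, with no new data and no change to procedures. The downside is more output that could be misread as testing.
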